9.1.3 Early Termination Visit

Every effort will be made to keep the participants in the study for the full study period. However, if a patient decides to discontinue the investigational product, the patient will be asked about the reason(s) for discontinuation and the presence of any AEs. If possible, the patient will be asked to complete the Day 42/Early Termination (ET) visit prior to discontinuation, and day 70 to assess safety. Following completion of the Early Termination Visit, the patient will either be treated by the investigator with standard of care or, should the patient choose, return to treatment by a prior/referring physician. In this case, the investigator will facilitate and coordinate follow-up to ensure continuity of care.

Participants who discontinue from the study will not be replaced.

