## 12.2 Adverse Events and Serious Adverse Event

### 12.2.1 Definition of Adverse Events

An AE is any untoward medical occurrence in a clinical study patient administered a medicinal (investigational or non-investigational) product. An AE does not necessarily have a causal relationship to the treatment. An AE can therefore be any unfavorable and unintended sign (including an abnormal finding), symptom, or disease temporally associated with the use of a medicinal (investigational or non-investigational) product, whether or not related to that medicinal (investigational or non-investigational) product.

This definition includes any occurrence that is new in onset or aggravated in severity or frequency from the baseline condition, or abnormal results of diagnostic procedures, including laboratory test abnormalities.

The following variables will be collected for each AE:

- AE (verbatim)
- The date and time when the AE started and stopped
- Maximum intensity or changes in intensity
- Whether the AE is serious or not (see Section 12.2.4)
- Expectedness
- Investigator assessment of relationship to investigational product
- Action taken with regard to the investigational product (uptitration, downtitration, temporarily discontinued, permanently discontinued or no action taken)
- AE caused patient's withdrawal from the study (yes or no)
- Outcome

Adverse events will be collected from the time of signature on the informed consent form throughout the Follow-up visit or early termination. Whenever possible, diagnoses will be given when signs and symptoms are due to a common etiology (e.g., cough, runny nose, sneezing, sore throat, and head congestion will be reported as “upper respiratory infection”).

Worsening symptoms of the primary study condition (i.e., bipolar depression) will be recorded as a primary endpoint rating.

Any AE(s) that are unresolved at the follow-up visit (Day 70) will continue to be followed by the investigator for as long as medically indicated, but without further recording in the eCRF. The Contract Research Organization (CRO) and its representative retain the right to request additional information for any patient with ongoing AE(s)/SAE(s) at the end of the study, if deemed medically necessary.

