### **12.2.4 Definition of Serious Adverse Events**

The following criteria define an SAE:

- Death
- Life-threatening event
- Inpatient hospitalization  $>24$  hours or prolongation  $>24$  hours of inpatient hospitalization
- Persistent or significant disability/incapacity
- Congenital anomaly/birth defect
- Medically important event, as defined in this protocol\*

\*Medical and scientific judgment will be exercised in deciding whether expedited reporting is also appropriate in other situations, such as important medical events that may not be immediately life threatening or result in death or hospitalization but may jeopardize the patient or may require intervention to prevent one of the other outcomes listed in the definition above. These will usually be considered serious.

In addition, the following variables will be collected, where applicable, for SAEs:

- Date AE met criteria for SAE
- Date investigator became aware of SAE
- Description of SAE

- Explanation of seriousness of the AE
- Date of hospitalization
- Date of discharge
- Probable cause of death
- Date of death
- Autopsy performed
- Causality assessment in relation to investigational product
- Causality assessment in relation to other medication

It is important to distinguish between serious and severe AE(s). Severity is a measure of intensity, whereas seriousness is defined by these criteria. An AE of severe intensity need not necessarily be considered serious. If inpatient hospitalization results from worsening psychiatric symptoms or suicidal ideation, the hospitalization will be reported as an SAE.

SAEs will be reported from the time of informed consent through the Follow-up visit or early termination. Unsolicited SAEs will be collected up to 30 days after the last study treatment.

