### 17.1.4 Other Efficacy Endpoints

The following additional endpoints will be recorded and analyzed by treatment group:

- Dose per treatment group
- Suicide rates (attempted and completed)
- Time to all-cause study discontinuation (and reason for discontinuation) due to any reason such as withdrawal due to an adverse event, or patient or investigator decision to withdraw
- Rate of participants who achieve a resolution of suicide risk by Clinical Global Judgement of Suicide Risk [CGI-SS] 0 or 1) or by MADRS (suicidal ideation item #10 of 0 or 1)
- Percent in remission at Day 42/exit, defined as having achieved a MADRS score of  $\leq 10$  during the last two visits (14 days)
- Proportion of participants who are treated with new SSRIs or have increased SSRI dosages
- Proportion of participants who discontinue SSRIs or have reduced SSRI dosages

- Efficacy for each MADRS question as well as the three Borenstein factors.

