### **20.4 Other Efficacy Endpoints**

The following additional endpoints will be recorded and analyzed by treatment group for both study phases:

- Dose per treatment group
- Suicide rates
- Proportion of participants who are treated with new SSRIs or have increased SSRI dosages
- Proportion of participants who discontinue SSRIs or have reduced SSRI dosages
- Efficacy for each BPRS factor.

Dose per treatment group will be displayed graphically over time per study treatment group. The percent decreasing and increasing over time relative to starting dose will be displayed per study treatment group.

Time to all-cause study dropout will be displayed using a Kaplan-Meier lifetable.

The following three measures will be separately evaluated using a two-sided Fisher Exact test to compare treatments:

- the need to implement a new treatment plan.
- an increase in suicidal ideation (a score of  $\geq 4$  on the C-SSRS, emergent suicidality requiring hospitalization).
- an increase in depressive symptoms (a score increase of  $\geq 5$  from the previous on-study visit for two consecutive visits on the MADRS total score).

The number of hospitalization and ER visits per subject will be evaluated using a Wilcoxon Rank Sum test to compare each study treatment group.

The proportions of participants discontinuing SSRIs or reducing SSRI dosages will be displayed graphically over time per study treatment group. The percent discontinuing SSRIs and reducing SSRI dosages relative to starting dose will be displayed per study treatment group.

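### Hospitalization and ER-visit counts are compared without adjustment for time observed, so unequal dropout can bias the comparison

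*SAP*

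**What the plan says.** SAP 20.4 (Other Efficacy Endpoints) states that the number of hospitalizations and "ER visits per subject will be evaluated using a Wilcoxon Rank Sum test to compare each study treatment group". It names no start or end of observation, no analysis set, no exposure term and no handling of subjects who leave early. Protocol 16.8.8 plans the same test but calls the outcome an incidence. The SAP turns it into a count per subject, and under SAP section 13 the SAP governs.

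Four provisions determine how long a subject is observed:

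- SAP 12.2.1: "Adverse events will be collected from the time of signature on the informed consent form throughout the Follow-up visit or early termination".
- SAP 12.2.4, for serious events, which include inpatient stays over 24 hours: "SAEs will be reported from the time of informed consent through the Follow-up visit or early termination".
- SAP 12.2.4, after treatment ends: "Unsolicited SAEs will be collected up to 30 days after the last study treatment".
- Protocol 9.1.3, for patients who stop investigational product: "If possible, the patient will be asked to complete the Day 42/Early Termination (ET) visit prior to discontinuation, and day 70 to assess safety". The same section says that leavers are not replaced.

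The Schedule of Assessments (Table 1) has an adverse-event row running to Day 70 but no row for hospitalizations or ER visits. Adverse-event reporting is therefore the only visible source for these counts. SAP 17.1.4 also lists rates of attempted and completed suicide without stating a denominator.

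**The concern.** A subject observed for 14 days with no visit receives the same rank as one observed for 70 days with none. If the arms lose patients at different speeds, the comparison mixes how often events happen with how long each arm was watched.

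Unequal loss is plausible here. SAP 7.4 has a safety objective that fewer NRX-101 patients will be discontinued for lack of efficacy or worsening suicidality. SAP 12.2.6.2 calls for discontinuing patients judged at imminent risk of suicide. Some who leave may therefore be those most likely to need hospital care soon afterwards.

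What is at stake is the reading of one between-arm p-value on hospital and ER use. In a suicidal population that result will attract attention even though it is not a confirmatory test.

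**Working it through.** **Plan's own figure.** There is none to reproduce. Neither document gives an event rate, dropout rate or power statement for this comparison. The dropout and event rates below are assumptions.

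**Step 1: expected bias with equal true rates.** If events occur at the same constant rate in both arms, and exit is unrelated to the event, the ratio of expected counts equals the ratio of mean observed time. Assume a full window of 70 days and exits at Day 14.

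Mean observed days = (share staying × 70) + (share leaving × days observed if leaving)

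| Days observed if leaving | 25% leave | 10% leave | Ratio | Shortfall |
|---|---|---|---|---|
| 14 (collection stops at exit) | 0.75×70 + 0.25×14 = 56.0 | 0.90×70 + 0.10×14 = 64.4 | 0.87 | about 13% |
| 44 (all events in the next 30 days captured) | 0.75×70 + 0.25×44 = 63.5 | 0.90×70 + 0.10×44 = 67.4 | 0.94 | about 6% |
| 70 (Day 70 contact completed) | 70 | 70 | 1.00 | nil |

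With 20% against 10% leaving, the same arithmetic gives 58.8/64.4 = 0.91 (about 9%) and 64.8/67.4 = 0.96 (about 4%).

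**Step 2: effect on the planned test.** The Wilcoxon test compares ranks, so a percentage shortfall in counts is not itself the error in the test. Simulation used 37 per arm, identical Poisson rates of 0.1 or 0.3 events per subject over 70 days, exit times uniform over Days 0 to 42, and 2,000 runs per case. Two figures in a cell are for rates 0.1 and 0.3.

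| Dropout | Count ratio | Wilcoxon false positives | Person-time test false positives |
|---|---|---|---|
| 20% / 20% | 1.01, 1.00 | 6.7%, 4.0% | 2.3%, 3.3% |
| 30% / 15% | 0.90, 0.89 | 6.1%, 5.6% | 2.9%, 3.9% |
| 40% / 10% | 0.81, 0.78 | 7.1%, 8.4% | 2.8%, 4.3% |
| 40% / 10%, 30 days captured after exit | 0.90, 0.91 | 6.0%, 5.6% | 2.5%, 4.5% |

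The person-time test is an exact conditional rate test. The simulation error of a 5% rate is about √(0.05×0.95/2000) = 0.5 percentage points. At 40% against 10%, most false positives favour the arm that lost more patients: 5.7% and 7.7% of runs, where about 2.5% would be nominal in one direction. With person-time as denominator, the estimated rates agree between arms to within 0.004.

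**Step 3: when the hospitalization causes the exit.** Assume true rates of 0.3 and 0.1 over 70 days, exit at the first hospitalization, and 10% other dropout in both arms. Total exit is then 33% against 19%, and the observed counts are 0.24 against 0.09. With full follow-up, the share with at least one event would be 1−exp(−0.3) = 0.26 and 1−exp(−0.1) = 0.10. The arm that loses more patients shows more events, as it should. What is lost is mainly repeat events after exit.

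**The case against.** The best defence has four parts.

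- **Follow-up does not simply stop at exit.** A reader of SAP 12.2.1 and 12.2.4 might infer that it does. That overlooks the 30-day window and the Day 70 contact in Protocol 9.1.3. Both are real provisions, and together they could remove the bias. Neither guarantees equal follow-up, however: the first is passive and limited to serious events, so an ER visit that is not serious falls outside it, and the second is conditional.
- **The direction is not fixed.** A reader might infer that the arm with more dropout must show a falsely low count. The documents do not support this. Equal dropout gives no bias, and a hospitalization that ends participation is counted (Step 3).
- **The plan's time-to-treatment-failure alternative does not size the problem.** The hazard ratio of 0.421 in SAP 16.3 needs about 42 failures for 80% power; with 42, exp(−1.96×2/√42) = 0.546, close to the stated 0.545. One could translate this into 72% against 41.5% failing by Day 42 and, if failure ended observation, 31.6 against 48.9 observed days of 70, a 35% shortfall. Three things undercut that figure. The failure shares are back-calculated and appear nowhere in the plan. Capturing the 30 days after exit reduces the shortfall to about 13%: (31.6 + 0.72×30)/(48.9 + 0.415×30) = 53.2/61.4 = 0.87. And psychiatric hospitalization is part of treatment failure, so that hazard ratio is hard to combine with equal hospitalization rates.
- **Partly covered elsewhere.** Psychiatric hospitalization enters the time-to-treatment-failure analysis, and dropout is displayed by Kaplan-Meier. This stands, but it covers neither ER visits nor non-psychiatric admissions as separate outcomes, and the dropout display does not correct the count comparison.

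**Conclusion.** The point holds as a modest weakness in an analysis outside the hierarchy of SAP 18.3. SAP 20.4 compares raw counts, while the collection rules allow observed time to differ by subject. If dropout is unequal and events after exit are incompletely captured, the comparison is biased, usually downward in the arm with more dropout unless the hospitalization itself causes the exit.

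Under assumed dropout of 25% against 10% at Day 14, equal true rates and exit unrelated to the event, the bias lies between nil and about 13%, depending on how much is captured after exit. The effect on the test is small unless dropout differs sharply: 7% to 8% false positives at 40% against 10%, from a level of 4.0% to 6.7% when dropout is equal. How ER visits are recorded is not stated in either document; reliance on adverse-event reporting is inferred from Table 1. Likewise, the lack of an exposure denominator for suicide rates rests on the SAP's silence, not on a stated rule.

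**What to change.** In SAP 20.4:

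1. State one observation window for all subjects, for example Day 1 to Day 70 regardless of discontinuation, using the contact that Protocol 9.1.3 already requests. State the source for ER visits.
2. Report observed person-time by arm, from first dose to last contact. Say how unsolicited events reported after last contact are handled, so that numerator and denominator cover the same days.
3. Replace or supplement the Wilcoxon test with events per observed patient-time: a Poisson or negative binomial model with log observed days as offset, or an exact conditional rate test if events are few. Time to first hospitalization or ER visit, censored at last contact, is an alternative.
4. Give suicide attempts per patient-time in the same table.
5. Show reasons for exit by arm beside the result.

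The cost is SAP wording and a few lines of code. Exit times are needed anyway for the planned Kaplan-Meier display of dropout. There are two limits. With few events the estimates will be imprecise. And an offset or censoring assumes that exit is unrelated to the risk of the next event, so it does not cure informative dropout. Completing the Day 70 contact addresses that directly, and item 5 lets the reader judge what remains.

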## 20.5 Safety Endpoints

Adverse events will be classified by MedDRA. For each study treatment, safety data will be collected and analyzed while on treatment or until treatment-emergent adverse events are resolved. The type, incidence, timing (onset, duration), relationship, and severity of AEs will be reported for treatment-emergent and SAEs. Reasons for withdrawal due to AEs will also be reported. Narratives will be written for every AE classified as serious or associated with attempted suicide or death.

Safety and tolerability will be assessed using two-sided Fisher Exact tests to compare overall adverse event incidence for NRX-101 vs. lurasidone. Mean changes from randomization baseline will be displayed for each serum chemistry and hematology parameter as well as the shift; unpaired t-tests will be used to compare treatments. In addition, paired t-tests will be performed for the changes from randomization baseline for each study treatment group.

C-SSRS will also be considered as a safety endpoint but will be analyzed as a McNemar paired comparison test within treatment groups and as a Jonchkeere-Terpstra test to compare treatment groups.

Vital signs and ECGs (means and mean changes from baseline will also be evaluated within treatment groups using paired t-tests and between study treatment groups using unpaired t-tests. Percent with abnormal vital signs, heart rate, QRS duration, PR interval, RR interval, QT, and QTcF will be reported. McNemar paired comparison tests will be performed within study treatment groups for the abnormal discordant percent while two-sided Fisher Exact tests will be performed to compare incidences between treatment groups.

Blood draws for chemistries and hematologies will be evaluated within and between study treatment groups. Abnormality rates will be presented relative to established site-specific normal ranges and whether or not the abnormality is clinically significant. McNemar paired comparison tests will be performed within study treatment groups for the abnormal percents while two-sided Fisher Exact tests will be performed to compare incidences between treatment groups.

## 22. APPENDICES

### Appendix 1: Concomitant Medications

Medications Allowed (Y) and Not Allowed (N) as Concomitant Medications

Drug Name or Class	Episodic Use (PRN)	Chronic Use	Restrictions/Comments
Analgesics	Y	Y	Nonnarcotic analgesics are allowed. Medically appropriate episodic use of narcotic analgesics is allowed for acute medical indications but is limited to no more than three days for each episode. Chronic NSAID use is exclusionary; tramadol is also not allowed.
Anesthetics, general	Y (except for ketamine, which is excluded)	—	If procedures requiring general anesthesia are to occur/have occurred, please contact Medical Monitor to report the medical condition(s).
Anesthetics, local	Y	N	—
Anorexics	N	N	—
Antacids	Y	Y	—
Antiacne	Y	Y	Topical agents only, including topical antibiotics. Isotretinoin (Accutane) is not allowed.
Antiangular agents	N	N	—
Antiarrhythmics	N	N	Amiodarone is excluded.
Antiasthma agents	Y	Y	—
Antibiotics	Y	Y	Chronic use of topical antibiotics for acne is allowed, with the exception of the MAOI linezolid (Zyvox) and isoniazid, which are not allowed. Nafcillin, Erythromycin, clarithromycin, rifampin are excluded.
Anticoagulants	N	N	Warfarin (Coumadin) is not allowed. Antiplatelet agents are allowed (see "Antiplatelets").
Anticholinergics	Y	Y	Except for scopolamine.

Drug Name or Class	Episodic Use (PRN)	Chronic Use	Restrictions/Comments
Anticonvulsants	N	Y	Gabapentin, lamotrigine and pregabalin are allowed. Other anticonvulsants are not allowed, including carbamazepine and oxcarbamazepine, phenytoin, phenobarbital, rufinamide (CYP3A4 inducers). Stable in dosing at least four weeks prior to randomization is required.
Antidepressants	N	Y	Stable (for at least 4 weeks prior to screening), ongoing antidepressant therapy is required during the course of the study. No dose changes are allowed during the study. Monoamine oxidase inhibitors (which may have unknown drug-drug interactions) are excluded. Concomitant use of trazodone (up to 200mg daily) is allowed. Nefazodone and St John's Wort are excluded (CYP3A4 inhibitor, inducer, respectively).
Antidiarrheal preparations	Y	N	Only loperamide HCl (Imodium), bismuth subsalicylate (Pepto-Bismol), and kaolin preparations are allowed.
Antifungals, systemic	N	Y	Ketoconazole, itraconazol, rifampin and rifabutin are excluded.
Antifungals, topical	Y	Y	Ketoconazole and itraconazole are excluded.
Antihistamines	Y	Y	The use of combinations containing pseudoephedrine or phenylephrine is not allowed. Combination products containing the word nighttime or are specifically marketed for before sleep routinely include an antihistamine and are not allowed. Combination products ending in “-D” routinely contain a stimulant such as phenylephrine, and the appropriate limits above apply to them. (See “Cough and Cold Preparations” for combination products.)
Antihypertensives	N	Y	Diltiazem, verapamil are excluded.
Anti-impotence medications	Y	Y	—
Anti-inflammatory drugs	Y	Y a	Indomethacin (Indocin) and systemic corticosteroids are not allowed. Chronic NSAID use is exclusionary.
Antimigraine	N	N	Triptans are not allowed.

Drug Name or Class	Episodic Use (PRN)	Chronic Use	Restrictions/Comments
Antinauseants/Antiemetics	Y	N	Phosphoric acid preparations (Emetrol, Emecheck), bismuth subsalicylate (Pepto-Bismol), cola syrup, 5-HT 3 receptor antagonists (e.g., ondansetron), and prokinetic agents (metoclopramide) are allowed. Scopolamine is not allowed (see section on anticholinergic).
Antineoplastics/Immunosuppressant agents	N	Y c	Interferons, methotrexate, and other immunosuppressant agents are not allowed. Call Medical Monitor for approval for certain cases in cancer remission maintaining therapy.
Antiobesity/Appetite suppressants	N	N	OTC Alli (Xenical), sibutramine (Meridia), and phentermine (Adipex-P and others) are not allowed.
Antiplatelet agents	N	Y b	Aspirin (maximum 325 mg/day) and clopidogrel (Plavix) are allowed. Note that use of an SSRI or of a triple uptake inhibitor may increase bleeding times and possibly prothrombin times.
Antipsoriatic treatments	Y	Y	Only topical agents are allowed. Acitretin (Soriatane) is not allowed.
Antipsychotics	N	Y	Stable in dosing at least four weeks prior to randomization is allowed. Lurasidone will be discontinued at study entry. Quetiapine, aripiprazole, risperidone, brexpiprazole, olanzapine, cariprazine, or lumateperone should be discontinued prior to randomization.
Antismoking medications	N	Y c	Varenicline (Chantix) is not allowed. Chronic nicotine replacement may be allowed in certain cases after review with Medical Monitor.
Antiviral agents	Y	Y	Only oral or topical agents are allowed. Only acyclovir, famciclovir, valacyclovir, penciclovir, docosanol, trifluridine, and vidarabine are allowed. Amantadine, rimantadine, and protease inhibitors (atazanavir, darunavir, indinavir, lopinavir, nelfinavir, ritonavir, saquinavir, tipranavir) are not allowed. Tamiflu (oseltamivir phosphate), and Relenza (zanamivir) inhalants are permitted for influenza prophylaxis but use is limited to a 7- to 14-day course in accordance with prescribing information. Interferons are not allowed.
Anxiolytics	N	Y	Chronic, stable treatment with benzodiazepines is allowed. Stable in dosing at least four weeks prior to randomization is required.
Barbiturates	N	N	Barbiturates are not allowed.

Drug Name or Class	Episodic Use (PRN)	Chronic Use	Restrictions/Comments
Benign prostatic hyperplasia treatments	N	Y b	Male patients who have symptoms of obstructed voiding should not be included in the study. Surgically or medically treated patients must be asymptomatic and receiving a stable dosage of allowed medications ( $\alpha$ -1 blockers, finasteride, or dutasteride) for one month before screening.
Buspirone	N	Y	Stable in dosing at least four weeks prior to randomization is allowed.
Cough/cold preparations	Y	N	Use of cough and cold preparations containing pseudoephedrine or dextromethorphan is not allowed, as are those containing phenylephrine. Combination products ending in “-D” routinely contain a stimulant such as phenylephrine, and the appropriate limits apply to them. (See “Antihistamines”.)
Diuretics	Y	Y b	Episodic use of diuretics is restricted to treatment of premenstrual symptoms. For chronic use, medication and dosage should be stable for 1 month before screening.
Dopaminergics	N	Y	Dopamine agonists for restless leg syndrome are allowed.
Ethyl alcohol	N	N	Participants should not use alcohol during the course of the trial because ethyl alcohol may increase the possibility and risks of seizures in participants receiving cycloserine.
Gastrointestinal: 
 
• H2-blockers/
 
• proton pump inhibitors/
 
• prokinetic agents
 
	Y	Y	Cimetidine (Tagamet) is not allowed. Metoclopramide is not allowed.
Hormonal (noncontraceptive) therapies	N	Y	See below.
Hormone suppressants	N	Y b	Only finasteride (Proscar) and dutasteride (Avodart) are allowed.
Hormones: reproductive	N	Y	Systemic hormonal contraceptives (oral contraceptives of estrogen and progestin combinations, depot injections such as Depo-Provera, the contraceptive implant Implanon, and/or transdermally delivered contraceptives such as Ortho Evra) are allowed.

Drug Name or Class	Episodic Use (PRN)	Chronic Use	Restrictions/Comments
Hormones: thyroid	N	Y	Thyroid hormone replacement is allowed (dosage of thyroid medication should be stable for three months before screening). Therapeutic use for psychiatric disorders (e.g., T3 augmentation) is not allowed.
Hypoglycemic agents	N	Y	Oral hypoglycemic agents are allowed. Insulin is allowed.
Hypolipidemics	N	Y b	Ezetimibe (Zetia) is allowed.
Hypolipidemics: bile acid sequestrants	N	N	—
Hypolipidemics: fibrates	N	Y b	Gemfibrozil and fenofibrate are allowed
Hypolipidemics: niacin	N	N	Niacin and niacinamide are not allowed.
Hypolipidemics: statins	N	Y b	Lovastatin, simvastatin, pravastatin, atorvastatin, fluvastatin, and rosuvastatin are allowed.
Laxatives	Y	Y a	Only fiber-based products and docusate sodium (Colace) are allowed.
Lithium	N	Y	Stable in dosing at least four weeks prior to randomization is allowed.
Medications that are primarily metabolized by CYP2C8 (e.g., cerivastatin, paclitaxel, repaglinide, sorafenib, and torsemide)	N	N	—
Muscle relaxants	N	N	—
NMDA receptor antagonist	N	N	Memantine is excluded.
Opioid agonists/analgesics (e.g., codeine, hydrocodone, methadone, morphine, maperidine, propoxyphene) and antagonists (e.g., naltrexone, naloxone, nalmefene)	N*	N*	See section on analgesics for exceptions.
Sedatives/hypnotics	N	Y	Ongoing, stable hypnotic therapy (e.g., zolpidem, zaleplon, benzodiazepine hypnotics, and low-dose trazodone 50-200mg) will be allowed during the course of the study. Eszopiclone is not allowed.

Drug Name or Class	Episodic Use (PRN)	Chronic Use	Restrictions/Comments
Steroids/systemic	Y	N	Systemic steroid treatment will be allowed only for medical emergencies, such as severe allergic reactions.
Steroids/topical and inhalant	Y	Y	—
Steroids/intra-articular	Y	NA	—
Stimulants	N	N	Oral or transdermal methylphenidate, amphetamine products or prodrugs, pseudoephedrine, modafinil (Provigil), and other medications of same category are not allowed.
Vaccines	Y	NA	—

- a If being taken prior to enrolling in the study.
- b If being taken for at least three months prior to enrolling in the study and the dose has been stable for at least 1 month.
- c If approved by Medical Monitor5-HT3 = 5-hydroxytryptamine receptor type 3; 5-HTP = 5-hydroxytryptophan; ACE = angiotensin-converting enzyme; CR = controlled release; DHEA = dehydroepiandrosterone; N = no; NA = not applicable; OTC = over the counter; PRN = as needed (prorenataT3prorenataT3=triiodothyronine; Y = yes.

---

